**Statistical Analyses:**

Demographic and clinical data: Independent-sample t-tests will be performed to compare the baseline values between the PD-neurofeedback and PD-control groups ( $p < 0.05$ , two-tailed).

**Aim 1:** A 2x2 mixed ANOVA with an interaction term will be performed to assess group differences in right insula-dmFC functional connectivity (between-subject factor: group, within-subject factor: right insula-dmFC functional connectivity during the first and last control scan, interaction: group x insula-dmFC functional connectivity). Post-hoc tests will be Bonferroni-corrected,  $p < 0.05$ .

**Aim 2:** Within-group one-sample t-tests will be performed on the right insula and dmFC resting-state functional connectivity maps. A 2x2 mixed ANOVA with an interaction term will be performed to assess group differences in resting-state functional connectivity (between-subject factor: group, within-subject factor: resting-state functional connectivity pre- and post-intervention, interaction: group x resting-state functional connectivity). All group analyses will be corrected for multiple comparisons using the false discovery rate procedure ( $p < 0.05$ , two-tailed) (Genovese et al., 2002).

**Aim 3:** The scores (i.e., time required for completion) of the motor function tests will be z-transformed and summed to obtain a composite motor function score for each subject. A 2x2 mixed ANOVA will be performed to compare the differences in motor functioning between the groups pre- and post-training (between-subject factor: group, within-subject factors: MDS-UPDRS motor exam and composite motor function scores, interaction: group x motor assessment). Post-hoc tests will be Bonferroni-corrected,  $p < 0.05$ .

**Exploratory Aims:** A paired-sample t-test will be performed to assess the differences in the whole-brain functional connectivity associated with the imagery and video-watching tasks. The results will be corrected for multiple comparisons using the false discovery rate procedure ( $p < 0.05$ , two-tailed) (Genovese et al., 2002).

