**Power analysis:** The sample size calculation is based on the clinically important difference (CID) in the primary motor outcome measure. Approximately a 5-point decrease in the mean MDS-UPDRS motor exam score after an intervention has been defined as a moderate CID (Schrag et al., 2006; Shulman et al., 2010). In this study, we expect a moderate CID. We used the mean and standard deviation of the MDS-UPDRS motor exam scores ( $24 \pm 9$ ) of a large group of subjects with PD (N = 347) as the population mean and standard deviation (Shulman et al., 2010). Assuming  $\alpha = 0.05$  and power = 0.80, 22 subjects are required for a moderate CID. Considering the possibility of a 35% drop-out rate between Visits 1 and 4, we will plan to recruit 30 subjects each for the PD-neurofeedback and PD-control group, total of 60 subjects. We will also perform an adaptive interim statistical analysis based on the primary motor outcome (Bauer and Kohne, 1994). If the p values fall between 0.023 (efficacy boundary) and 0.5 (futility boundary), then we will recalculate the sample size based on conditional power (e.g., 0.80). If the p value is  $< 0.023$  (i.e., significant difference) or  $> 0.5$  (i.e., no hope to find a significant difference), we will terminate the study.

**Randomization:** Group assignment of subjects will be determined by the end of Visit 1. We will use a covariate adaptive randomization method (Lin et al., 2015). Age and gender are important variables and need to be controlled during randomization. This method will take into account age and gender and sequentially assign each new subject accordingly. This approach will allow us to balance the two groups in terms of age and gender.

**Potential problems:** 1) Variability in neurofeedback learning will be expected. We aim to reduce variability by providing personalized and detailed motor imagery scripts and facilitate learning with homework. 2) In general, attrition rate can be an issue especially in control groups. Our active control design will help minimize this by controlling for subject engagement in tasks during visits and at home, and for time spent with research staff.

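### Age and gender drive the allocation but appear in none of the Aim 1–3 models; where they predict the quantity analysed, the group tests are conservative and lose some power

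*Combined protocol and SAP*

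**What the plan says.** Section 13, Randomization, gives the rationale, "Age and gender are important variables and need to be controlled during randomization", and the method, "We will use a covariate adaptive randomization method", and adds: "This method will take into account age and gender and sequentially assign each new subject accordingly". It does not name the algorithm, the age categories or the assignment probability.

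Section 13, Statistical Analyses, sets out mixed ANOVAs with these factors:

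- Aim 1: "between-subject factor: group, within-subject factor: right insula-dmFC functional connectivity during the first and last control scan", plus their interaction.
- Aim 2: "between-subject factor: group, within-subject factor: resting-state functional connectivity pre- and post-intervention", plus their interaction.
- Aim 3: "between-subject factor: group, within-subject factors: MDS-UPDRS motor exam and composite motor function scores, interaction: group x motor assessment". The sentence speaks of comparing the groups before and after training, but the listed within-subject factors are the two motor scores, not time.

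No age or gender term, other covariate adjustment or re-randomisation test appears anywhere in the document. The interim rule in the power paragraph acts on a p value for the primary motor outcome, with boundaries at 0.023 and 0.5, and does not say which model produces it.

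**The concern.** Balancing the groups on a prognostic variable removes that variable's contribution to the true sampling variance of the group difference. A model that omits the variable still counts its contribution as residual error. The reported standard error is then too large, the p value too high and the power lower than the same data could give. This matters more in a trial of 60 recruits with up to 35% drop-out, and where an interim decision to stop rests directly on a p value: an over-large p value makes the efficacy boundary harder to reach and the futility boundary easier to cross.

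**Working it through.** **The plan's own figure.** The plan says "and power = 0.80, 22 subjects are required for a moderate CID", from a 5-point difference and SD 9. That number reproduces only as a one-sample, one-sided t-test. A two-sample, two-sided comparison with the same inputs needs 51 per group by the normal approximation. That is a separate matter. What counts here is that no version of the calculation contains a term for age, gender or balancing.

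**Inputs**

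- From Section 13: difference 5, SD 9 (d = 5/9 = 0.56), alpha 0.05.
- Assumed: two-sided testing; 22 completers per group, 44 in all (the plan does not say whether its 22 is per group); SD 9 for the analysed quantity, although the protocol gives it as the SD of scores, not of change; R² of 0 to 0.20. The simulations also assume minimisation with assignment probability 0.8.

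**Step 1: which tests are exposed.** With two time points, the group-by-time test is the two-sample t-test on change, so any age or gender effect on level cancels. A simulation with 44 subjects had age and gender explain 30% of level and none of change, with an assumed pre/post correlation of 0.8, so SD of change = 9 × √(2 × 0.2) = 5.7:

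- Interaction: size 0.048 unadjusted, 0.050 adjusted; power 80.6% and 80.1%.
- Between-subject group effect: size 0.025 unadjusted, 0.043 adjusted.

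The pre/post interaction is therefore unaffected unless age and gender predict change. A between-subject group effect is affected through level.

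**Step 2: size of the effect when they predict the analysed quantity.** Under perfect balance (normal approximation, n per group):

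- Reported SE = SD × √(2/n) = 9 × √(2/22) = 2.714.
- True SE = reported SE × √(1 − R²).
- True size of the unadjusted test = 2[1 − Φ(1.96/√(1 − R²))].
- Power unadjusted = 1 − Φ((1.96 × reported SE − 5)/true SE).
- Power adjusted = 1 − Φ(1.96 − 5/true SE).

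Example at R² = 0.10: true SE = 2.714 × 0.9487 = 2.574. Size = 2[1 − Φ(2.066)] = 0.039. Power unadjusted = 1 − Φ((5.319 − 5)/2.574) = 45.1%. Power adjusted = 1 − Φ(1.96 − 1.942) = 49.3%.

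| R² | Size, formula | Power unadjusted | Power adjusted | Gain, formula (points) | Size, simulated | Gain, simulated (points) |
|---|---|---|---|---|---|---|
| 0 | 0.050 | 45.3% | 45.3% | 0 | about 0.046 | about 0 |
| 0.05 | 0.044 | 45.2% | 47.2% | 2.0 | about 0.043 | about 1 |
| 0.10 | 0.039 | 45.1% | 49.3% | 4.2 | about 0.039 | about 4 |
| 0.20 | 0.028 | 44.8% | 54.0% | 9.2 | about 0.033 | about 8 |

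The simulated columns use d = 0.56 and 44 subjects. Their effects at R² = 0.20 are a little smaller because minimisation does not balance perfectly.

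The result does not hinge on SD 9. If the SD of change is about 5.9, the value at which 22 per group gives 80% power, the formula gives 80.6% against 82.0% at R² = 0.05, 81.2% against 84.0% at 0.10 and 82.7% against 87.9% at 0.20.

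**Step 3: the interim p value.** With the same approximation, an unadjusted two-sided p with normal deviate z has true tail probability 2[1 − Φ(z/√(1 − R²))]. A reported 0.023 corresponds to about 0.017 at R² = 0.10 and 0.011 at 0.20. A reported 0.5 corresponds to about 0.48 and 0.45.

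**The case against.** The strongest reply is that Aims 1 and 2 test change between two scans, so only an age or gender effect on the response to a 4–5 week programme would matter, and nothing in the protocol quantifies one. Calling the two variables important for allocation is not evidence that they predict training response. This stands, and it limits the point to a conditional one. A second reply is that the omission is a loss of efficiency and not a validity defect, and that balanced groups are a stated aim in their own right. That also stands.

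A reader might infer three stronger things that the documents do not support:

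- **That all the planned tests are conservative.** For a pre/post interaction with covariates that predict only level, they are not (0.048 against a nominal 0.05).
- **That the trial forfeits power its design had already secured.** The sample-size calculation takes no credit for balancing or adjustment.
- **That false positives or bias result.** Any error in size is in the conservative direction, and the estimated difference is not biased by the omission.

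The reply does not dispose of Aim 3. As worded, time is not among its within-subject factors. If its inference rests on a between-subject group effect, age and gender effects on level matter as well, and this is the aim that carries the outcome used for the sample size.

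**Conclusion.** The omission is a fact for all three aims; its consequence is conditional and probably small. Under the assumptions listed, the unadjusted test has a true size between about 0.05 and 0.03, and adjustment adds about 0 to 8 power points as R² of the analysed quantity goes from 0 to 0.20, with 1 to 4 points at 0.05 to 0.10. These figures rest on an R² that the documents do not supply, on 44 completers and on an assumed minimisation scheme. The exposure is clearest for Aim 3 if it is read as a between-subject comparison, and for the interim p value if R² is not negligible. The change is worth making because it costs almost nothing and matches the analysis to the allocation.

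**What to change.** In Section 13, pre-specify age (continuous) and gender as covariates in the Aim 1, Aim 2 and Aim 3 between-group models. For pre/post models, either analyse change with the two covariates or include covariate-by-time terms; covariate main effects alone leave the group-by-time test unchanged. State that the interim p value comes from the same adjusted model. In Aim 3, make clear whether the test of interest is group by time or a between-subject group effect.

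The cost is a sentence or two of text and two degrees of freedom (44 − 4 = 40 instead of 44 − 2 = 42 residual in the change model). Both variables are already collected for allocation. If they turn out not to be prognostic, the power loss is about half a point or less (80.6% against 80.1% in Step 1).

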**SECTION II: RESEARCH INVOLVING DRUGS, BIOLOGICS, RADIOTRACERS, PLACEBOS AND DEVICES**

*If this section (or one of its parts, A or B) is not applicable, check off N/A and delete the rest of the section.*

## A. RADIOTRACERS

 N/A

*Write here*

## B. DRUGS/BIOLOGICS

 N/A

## B. DEVICES

 N/A

**SECTION III: RECRUITMENT/CONSENT AND ASSENT PROCEDURES**

## 1. Targeted Enrollment: Give the number of subjects:

- a. Targeted for enrollment at Yale for this protocol: **70 subjects with PD**
- b. If this is a multi-site study, give the total number of subjects targeted across all sites: N/A

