**Exploratory Aim 1: To examine the functional connectivity of brain networks associated with hybrid mental imagery.**

We will recruit a new cohort of PD patients who will practice imagery of everyday task performance (e.g., preparing a meal, grocery shopping) in the MRI scanner. The imagery task will include motor and visual components. We will measure the functional connectivity of brain networks subserving hybrid mental imagery.

**Exploratory Aim 2: To compare the functional connectivity of brain networks during imagining versus observing the performance of everyday tasks.**

The same new PD cohort in Exploratory Aim 1 will also watch brief video footage of everyday task performance in the MRI scanner. We will compare the functional connectivity of brain networks

involved in hybrid mental imagery of everyday task performance with those recruited during observation of the actual task performance.

2. **Probable Duration of Project:** State the expected duration of the project, including all follow-up and data analysis activities.

2 years

3. **Background:** Describe the background information that led to the plan for this project. Provide references to support the expectation of obtaining useful scientific data.

[figure not shown]

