## 2. Research Strategy

### 2.1. Overview:

This study is a Phase II randomized clinical trial. We plan on recruiting a total of 60 subjects with PD via the support group chapters of the local advocacy group Connecticut Advocates for Parkinson's and the Yale Movement Disorders Clinic. All subjects will undergo MRI safety and medical history screening. Eligible subjects will be randomized into two groups: PD-neurofeedback and PD-control. Subjects in both groups will complete four visits in about 4-5 weeks, but only the PD-neurofeedback group will receive fMRI-based neurofeedback training. All testing and scanning will take place at the Yale Magnetic Resonance Research Center (MRRC). The timeline of the experimental protocol is shown in Figure 2.

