**3. Research Strategy for the Exploratory Aims:**

**Subjects:** We plan on recruiting 15 new subjects with PD. Subjects who are interested in participating in the study will undergo medical history and MRI screening for eligibility in-person or via phone/email. The standard MRI Safety Questionnaire that was developed at the MRRC will be used. All experimental procedures will be completed in one research visit. Subjects will continue to take their PD medications as scheduled throughout the research visit.

**Clinical Evaluation:** [name] will perform an initial physical and neurological examination on all subjects. The diagnosis of idiopathic PD will be made according to the UK Brain Bank diagnostic criteria (Hughes et al., 1992). The Movement Disorders Society-Unified Parkinson's Disease Rating Scale (MDS-UPDRS) (Goetz et al., 2008) and Hoehn & Yahr staging (Hoehn and Yahr, 1998) will be used to determine disease severity and stage of PD subjects. The Montreal Cognitive Assessment test will be administered to rule out dementia (Nasreddine et al., 2005). Self-evaluation questionnaires will be administered including: Beck Depression Inventory-II (Beck 1997), Starkstein Apathy Scale (Starkstein et al., 1992), Spielberger State-Trait Anxiety Inventory (Spielberger et al., 1982), Parkinson disease Fatigue Scale (Brown et al., 2005), Parkinson disease quality of life scale (PDQ39) (Peto et al., 1995), and Self-Efficacy (Chen et al., 2011) and Self-Regulation (Schwarzer et al., 1999) scales. Imagery skills will be tested using the Questionnaire on Mental Imagery (Sheehan 1967).

**Hybrid Mental Imagery Practice:** Subjects will practice guided mental imagery of everyday task performance outside the scanner.

**Video-Watching Practice:** Subjects will watch sample video footage of everyday task performance outside the scanner for practice.

**MRI Parameters:** We will conduct the MRI experiments in a Siemens 3.0 Tesla human research

magnet in the MRRC. A 32-channel head coil will be used to collect high-resolution anatomical and echo planar images for fMRI. First, T1-weighted MPRAGE anatomical images (voxel size: 1 x 1 x 1 mm) will be collected for an accurate localization of the fMRI data. Then, axial, T2-weighted, echo planar functional images will be collected (voxel size: 3.5 x 3.5 x 4 mm, 36 slices, FoV: 224 mm, TR: 2000 ms, TE: 25 ms, flip angle: 90°). The number of acquisitions will be 120 (4 min) for each mental imagery and video-watching session.

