E. Can donor-subjects withdraw their materials at any time, and/or withdraw the identifiers that connect them to their materials? *Write here*

- i. How will requests to withdraw materials be handled (e.g., material no longer identified: that is, anonymized) or material destroyed)? *Write here*

F. Describe the provisions for protection of participant privacy *Write here*

G. Describe the methods for the security of storage and sharing of materials *Write here*

6. **Subject Population:** Provide a detailed description of the types of human subjects who will be recruited into this study.

There is no restriction for gender, race, or ethnicity. Fifty subjects with PD will be recruited for this study. The median age of onset of idiopathic PD is 62.4 years. In the US, the incidence of PD cases before age 40 is extremely low (Wirdefeldt et al., 2011). Therefore, individuals below the age of 40 will not be included. PD affects more males than females with a median 1.8:1 male:female ratio (Wirdefeldt et al., 2011). We will aim to reflect this ratio in subject selection. Local and non-local patients with PD are referred to our outpatient clinics. We will seek a racially and ethnically diverse enrollment. A cross-sectional epidemiological study based on Medicare records (Willis et al., 2010). 61 reported the following ratios for racial distribution of PD in the US: White:Black = 1.5 and White : Asian = 1.4. Hispanic was treated as a racial category and the White (non- Hispanic):Hispanic ratio was 1. The number of other racial categories was very small. The numbers in the planned enrollment table below were calculated based on these ratios.

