### Planned Enrollment

	Not Hispanic or Latino		Hispanic or Latino		Total
Racial Category	Female	Male	Female	Male	
Asian	4	8	0	0	12
Black or African American	7	11	0	0	18
White	7	13	4	6	30
Total	18	32	4	6	60

7. **Subject classification:** Check off all classifications of subjects that will be specifically recruited for enrollment in the research project. Will subjects who may require additional safeguards or other considerations be enrolled in the study? If so, identify the population of subjects requiring special safeguards and provide a justification for their involvement.

 Children	 Healthy	 Fetal material, placenta, or dead fetus
 Non-English Speaking	 Prisoners	 Economically disadvantaged persons
 Decisionally Impaired	 Employees	 Pregnant women and/or fetuses
 Yale Students	 Females of childbearing potential	

NOTE: Is this research proposal designed to enroll children who are wards of the state as potential subjects?

Yes  No

8. **Inclusion/Exclusion Criteria:** What are the criteria used to determine subject inclusion or exclusion?

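### Total enrolment is stated inconsistently: the target is 70, the two planned cohorts add up to 75, and the population section says fifty

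*Combined protocol and SAP*

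**What the plan says.** The size of the study appears in six places in the combined protocol and SAP.

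- Section I, item 4, heading 2.1 (Overview), on the randomised trial: "We plan on recruiting a total of 60 subjects with PD".
- Section I, item 13 (Power analysis), after the drop-out allowance: "we will plan to recruit 30 subjects each for the PD-neurofeedback and PD-control group, total of 60 subjects".
- Section I, item 6 (Subject Population), text: "Fifty subjects with PD will be recruited for this study".
- The planned enrolment table under the same item 6, bottom row: "Total 18 32 4 6 60".
- Section I, item 4, heading 3 (Research Strategy for the Exploratory Aims): "We plan on recruiting 15 new subjects with PD". Exploratory Aim 1 in the Statement of Purpose says the same of this group: "We will recruit a new cohort of PD patients".
- Section III, item 1 (Targeted Enrollment): "70 subjects with PD". The multi-site line beneath it is marked not applicable, so no other site supplies further subjects.

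No section explains how 70 or fifty was obtained.

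**The concern.** The target in Section III is the only figure offered for the protocol as a whole, so it should equal the sum of the cohorts that the protocol plans. It does not. The exploratory cohort is described as new both times it is introduced, so it cannot be drawn from the 60 randomised subjects, and the two sizes have to be added.

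Item 6 adds a second conflict within one section: its text and its table disagree by 10.

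What is at stake is a basic planning figure. Depending on the section consulted, the study has 50, 60 or 70 subjects, or 75 if the cohorts are added. Anyone judging whether recruitment is complete, or reporting planned against actual enrolment, has no single number to work from.

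**Working it through.** **Inputs.** Randomised trial 60 (overview; power analysis, 30 per group; table). Exploratory cohort 15 (exploratory research strategy). Population text 50 (item 6). Protocol target 70 (Section III, item 1).

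**Step 1: where the 60 comes from.** The power analysis starts from 22 subjects, read here as per group, and a 35% drop-out rate. Multiplying, 22 × 1.35 = 29.7, rounded up to 30 per group, and 2 × 30 = 60. This reproduces the plan's figure. The 60 is therefore a number to recruit, with the drop-out allowance already in it. Whether 22 is the right starting point, and whether this is the right way to inflate it, are separate questions.

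**Step 2: the table.** Rows: 12 + 18 + 30 = 60. Columns: 18 + 32 + 4 + 6 = 60. The table is internally consistent and matches the randomised trial alone, with no room for the exploratory cohort. Its two non-Hispanic columns sum to 18 + 32 = 50, but the item 6 sentence is not restricted to that group, so this does not explain the fifty.

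**Step 3: can 70 be reproduced?**
- 60 + 15 = 75, above the target by 75 − 70 = 5.
- 50 + 15 = 65, below the target by 5.
- 60 alone and 50 alone also miss it.

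No combination of the stated cohort sizes gives 70.

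**Step 4: what 70 would mean if it were a ceiling (an assumption, not a statement in the documents).**
- Keep 60 randomised: 70 − 60 = 10 exploratory subjects instead of 15, a loss of 5/15, or one third.
- Keep 15 exploratory: 70 − 15 = 55 for the randomised trial, and 55/2 = 27.5, so 27 to 28 per group instead of 30.

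**Step 5: what the 75 counts.** It adds numbers to be recruited. At the plan's own 35% loss, 60 recruited leaves 60 × 0.65 = 39 completers. Reading the 60 as completers would instead need 60/0.65 = 92.3, so 93 recruited, which the plan does not propose.

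**The case against.** The best defence is that this is a clerical mismatch with little statistical consequence. Section III states a target, not a maximum, and no section stops recruitment at 70 or reduces a cohort. A figure that was never updated would explain it equally well. The fifty is contradicted by the table beneath it. The exploratory aims carry no power requirement that 10 instead of 15 would breach. For the randomised trial, 30 per group at 35% loss leaves 19.5 and 27.5 leaves 17.9. Both are below 22, so the target of 70 is not what causes that shortfall. All of this stands, and it limits the point to an inconsistency in a planning figure. It does not remove the inconsistency, because 70 still matches nothing else in the document.

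A reader might infer more, without support in the text:

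- *That one cohort must be cut.* This needs 70 to be binding, which is nowhere stated.
- *That recruitment would stop at 50.* The table in the same section, the overview and the power analysis all give 60.
- *That people who fail the Visit 1 checks after consent widen the gap.* The protocol does not say whether they count towards the target, and gives no failure rate. The drop-out allowance runs from Visit 1, so it may already cover them.
- *That the target must reserve places for the interim recalculation.* The interim analysis can enlarge the trial or end it, and nothing requires an unknown increase to be held in advance.

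The rationale for the exploratory experiments also cites results already obtained in both groups, so actual accrual may differ from the plan. The documents do not show how many places remained.

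**Conclusion.** The inconsistency is real and certain as arithmetic. The plan states 50, 60 and 70, and its two separate cohorts sum to 75, which is 5 above the protocol target. This rests on two readings, both supported by the text: the exploratory subjects are additional to the 60, and the protocol runs at one site. The 75 is the planned recruitment before any change at the interim analysis.

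The loss of 5 exploratory subjects, or of 2 to 3 per randomised group, is conditional on 70 being enforced as a ceiling. The documents do not establish that, nor do they settle whether 70 is an outdated figure or a deliberate limit. The correction should be made in either case, because the total sample size is a figure the trial relies on.

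**What to change.** If both cohort sizes stand:

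1. Set Section III, item 1 to 75 recruited subjects, broken down as 60 for the randomised trial and 15 exploratory.
2. Replace the fifty in Section I, item 6 with the same total and breakdown.
3. Either extend the planned enrolment table to 75 or label it as covering the randomised cohort only.
4. Say whether the total counts consented or randomised subjects. The exploratory cohort is not randomised, so its counting rule needs its own words.

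If 70 is the intended total, keep it and restate the affected cohort, for example an exploratory cohort of 10.

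The 75 should not be called evaluable, because the 60 already contains the drop-out allowance, and that word would create a new conflict with the power analysis.

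The cost is a wording change and a corrected target for the ethics board. The design does not change if 75 is confirmed. If 70 is kept, the stated size of one cohort falls.
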